### 3. Assignment and intervention:

#### 3.1. Calculation of the sample size and the method of assignment:

Sample size calculation: A total of 196 patients will be enrolled in this study. The sample size is estimated as follows:

Previous studies have reported that the efficiency rate of metformin and simvastatin in the treatment of NAFLD is 36-52%. The investigators hypothesize that the efficiency rate of Compound Zhenshu Tiaozhi capsules will increase by 25% compared to standard drugs.

Statistical calculation:  $P_1 = 69\%$ ,  $P_2 = P_3 = 44\%$ ,  $P_4 = 10\%$ ,  $\delta = P_1 - P_2 = 25\%$ , with  $\alpha = 0.05$ , power = 0.80, and a bilateral test, of which  $w = \sqrt{\frac{\sum_{i=1}^m (P_{t,i} - P_{c,i})^2}{P_{c,i}}}$ , thus n will be equal to 44. Assuming that the rate of loss to follow up is 10%, each group will require 49 cases. Therefore, a total of 196 cases will be required for the four groups.

3.2 The method of assignment: [name], a staff member working in the Department of Statistics in Guangdong Pharmaceutical University, is responsible for generating random sequences using the SAS software. A total of 196 numbers from 1 to 196 will be randomly generated (Supplement 2). Newly diagnosed patients who meet the inclusion criteria will have a case number according to their order of enrollment (for example: case number of the first patient: 001, second patient: 002). They will then obtain the corresponding therapeutic regimens based on their case number with 1:1:1:1 ratio randomized tables. The first group is the TLC group; the second group is the TLC + metformin group (0.5 g, PO tid); the third group is the TLC + Compound Zhenzhu Tiaozhi capsules group (2.52 (four tablets), PO tid); the fourth group is the TLC + simvastatin group (20 mg, PO qn).

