3.4 Sample Size

A total of 196 patients will be enrolled in this study. The sample size is estimated as follows:

Previous studies have reported that the efficiency rate of metformin and simvastatin in the treatment of NAFLD is 36-52%. We hypothesize that the efficiency rate of Compound Zhenshu Tiaozhi capsules will increase by 25% compared to standard drugs.

Statistical calculation: $P_1 = 69\%$, $P_2 = P_3 = 44\%$, $P_4 = 10\%$, $\delta = P_1 - P_2 = 25\%$, with $\alpha = 0.05$,

power = 0.80, and a bilateral test, $n = \frac{\chi_{\alpha}^2 + \chi_{\beta}^2}{w^2}$, of which $w = \sqrt{\sum_{i=1}^m \frac{(P_{t,i} - P_{c,i})^2}{P_{c,i}}}$, thus n will be equal to 44.

Assuming that the rate of loss to follow up is 10%, each group will require 49 cases. Therefore, a total of 196 cases will be required for the four groups.

4. Evaluation of the Efficacy of Parameters and Predictors

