6.2 Per Protocol Set (PPS)

The PPS refers to the set of subjects who meet the inclusion criteria and complete the research project, which also means they comply with the research protocol, have good compliance, do not use banned substances during trial, and have completed the case report form (CRF). The PPS analysis is mainly used to assess primary efficacy.

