9.3 Processing of Missing Values

Results will be carried forward when primary outcome measures are absent, according to the following details:

-
1. If patients lack a fat attenuation value at the 6 months follow up and they do not show a response at the cessation of therapy, the results at cessation of therapy can be carried forward to the 6 months follow up.
 2. If patients withdraw from the study before cessation of the study, and continue without a response, the results of the last visit can be carried forward.
 3. If patients lack an intermediate visit of a fat attenuation value, but have results for insulin resistance, intestinal barrier function, and intestinal bacterial overgrowth, the previous results can be carried forward.
 4. If patients withdraw from the study because of a full recovery, the results of the last visit can be carried forward.

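### The stated 80% power is wrong: for 69% v 44%, two-sided 5%, 44 evaluable patients per group give about 66% power (71–72% if all 49 count)

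*Protocol*

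**What the plan says.** Protocol 3.1 and SAP 3.4 give the same inputs: P1 = 69% (capsules), P2 = P3 = 44% (metformin and simvastatin), P4 = 10% (TLC), a difference delta = P1 − P2 of 25 points, alpha 0.05, and "power = 0.80, and a bilateral test". The 44% is the midpoint of the cited range: "the efficiency rate of metformin and simvastatin in the treatment of NAFLD is 36-52"%. From these the documents conclude "thus n will be equal to 44. Assuming that the rate of loss to follow up is 10%, each group will require 49 cases", and so 196 patients over four equal groups.

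The SAP prints a chi-square effect-size formula in w. Neither document gives the value of w, the degrees of freedom, or whether n is a total or a per-group number. The primary endpoint is binary: the fat attenuation index does or does not fall by at least one grade.

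Two SAP sections bear on how many patients the primary analysis will contain. SAP 6.2 says "The PPS analysis is mainly used to assess primary efficacy". SAP 9.3 says "Results will be carried forward when primary outcome measures are absent".

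**The concern.** Every input to a two-proportion calculation is printed, so the 44 can be checked directly, and it looks too small for a 25-point difference around 50% with a two-sided 5% test. The comparison affected is the one the trial is sized on. SAP 2.2 makes comparison with metformin and simvastatin a primary objective. If the true power is well below 80%, a non-significant result against either drug will look like stronger evidence of no advantage than it is.

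**Working it through.** **Inputs** (Protocol 3.1, SAP 3.4): p1 = 0.69, p2 = 0.44, difference 0.25, two-sided alpha 0.05 (z = 1.960), power 0.80 (z = 0.842), 10% loss, equal allocation.

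**What reproduces.** The steps after 44 are right: 44/0.9 = 48.9, rounded up to 49, and 4 × 49 = 196.

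**What does not: n = 44.**

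- Unpooled: n = (1.960 + 0.842)² × [0.69 × 0.31 + 0.44 × 0.56] / 0.25² = 7.849 × 0.4603 / 0.0625 = 57.8, so 58.
- Pooled, with mean rate 0.565: n = [1.960 × √(2 × 0.565 × 0.435) + 0.842 × √0.4603]² / 0.25² = (1.374 + 0.571)² / 0.0625 = 60.5, so 61.
- Arcsine: 60.3, so 61.

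The same formulas with one-sided 0.05 give 45.5 to 47.6. That is closer to 44 but contradicts the stated two-sided test.

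**Where 44 may come from.** This cannot be established. One route takes the printed w for a single cell: w² = 0.25²/0.44 = 0.142. One-sided z values then give (1.645 + 0.842)²/0.142 = 43.5, so 44; two-sided values give 55.3, so 56. Such a w also treats the 44% as known, although it is estimated from a randomised arm of the same size. The conclusion does not depend on this route.

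**Power at the planned size.** By the pooled normal approximation:

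- n = 44: z = (0.25 × √44 − 1.374)/0.678 = 0.419, power 66.2%.
- n = 49: z = (0.25 × √49 − 1.374)/0.678 = 0.554, power 71.0%.

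Other tests, two-sided 5%, with exact binomial enumeration unless marked:

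| Test | 44 per group | 49 per group |
|---|---|---|
| Uncorrected chi-square | 65.9% | 72.1% |
| Fisher, or Yates-corrected chi-square | 56.9% | 64.7% |
| Unpooled z, normal approximation | 68.6% | 73.2% |
| Unpooled z, exact | 71.3% | 72.3% |

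As a check on the required size, exact chi-square power is 78.2% at 58 and 81.5% at 61.

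**Sensitivity to the comparator rate.** Over the documents' 36–52% range, each with +25 points, exact chi-square power is 64–71% at 44 and 72–74% at 49.

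**Difference detectable with 80% power.** At 44 per group it is about 29 points (73% v 44%: 80.2% exact, 79.9% approximate). At 49 it is about 27.5 points (71.5% v 44%: 80.3% exact, 79.6% approximate).

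**Size needed for the stated power.** With 10% loss, 58/0.9 gives 65 and 61/0.9 gives 68 per group, so 260 to 272 in total against 196.

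**The case against.** The strongest reply is that 44 per group does give 80% under other readings of the hypothesis. The text speaks of standard drugs in the plural and sets P2 = P3, and the SAP text I have stops at baseline characteristics, so an efficacy section may exist that I cannot see. Three readings reach 80% with an uncorrected test at two-sided 0.05:

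- Capsules against the two drug arms combined (44 v 88): 80.1%.
- Significance against at least one of the two drugs, unadjusted: about 80%.
- A four-group omnibus test on 3 degrees of freedom: 99.9%, because the 10% TLC rate dominates.

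These figures are sound, but neither document states any of the three analyses. Both define the difference as P1 − P2, and Protocol 4.4 compares the capsules with the other three groups. The reply does limit the finding to capsules against one drug. Capsules against TLC (69% v 10%) has over 99.9% power at 44. Beating both drugs has only about 52%.

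It is also fair that the origin of 44 is a guess. The SAP prints a sum of two chi-square terms rather than a squared sum of z values, and other readings of w also land near 44.

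Finally, one can argue that the error is modest because no analysis changes and a confidence interval would show the uncertainty. That softens the consequence but does not make the printed power correct.

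**Conclusion.** The concern holds: the power statement is wrong as written. On the plan's own inputs, 44 evaluable patients per group give about 66% power for capsules against one standard drug, and 71–72% if all 49 are evaluable. The risk of missing the planned effect is about 34% (1 − 0.66), or 28–29% at 49, instead of 20%.

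Both counts matter. The per-protocol emphasis in SAP 6.2 fits 44 after the planned loss, while the carry-forward rules in SAP 9.3 could bring the count up to 49.

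The headline figures assume an uncorrected chi-square test and no multiplicity adjustment. The finding does not depend on that choice of test: across the tests tabulated, power runs from 57% to 71% at 44 and from 65% to 73% at 49. This must be corrected because it concerns the primary endpoint and stands in both documents.

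**What to change.** Keep 196 patients and replace the power statement in Protocol 3.1 and SAP 3.4 with wording such as:

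> With 44 evaluable patients per group, the power to detect 69% v 44% in each comparison of capsules with one standard drug is about 66% (71–72% if all 49 are evaluable), using an uncorrected chi-square test at two-sided 0.05. Power is 80% for a difference of about 29 points (73% v 44%) with 44 per group.

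Replace the printed w formula with the two-proportion formula. If another primary test or comparison is intended, name it and restate the power for it.

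The cost is wording in two sections and a less favourable stated power; no patients are added. Keeping the 80% claim instead would take 260 to 272 patients.

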### 4. Endpoints:

#### 4.1 Primary endpoints

*Fat attenuation index:* The fat attenuation index will be used to assess the therapeutic efficacy. A normal fat attenuation index is defined as < 240 db/m, mild is 240-264 db/m, moderate is 265-294 db/m, and severity is > 295 db/m. The investigators will detect the fat attenuation index at 0, 1, 3, 6 months following treatment. Effective: fat attenuation index is reduced by a level or more (example: moderate to mild). Invalid: fails to meet the effective standard.

#### 4.2 Secondary endpoints:

(1) *Serum triglyceride*

(2) *Serum cholesterol*

(3) *Serum lipoproteins:* chylomicron (CM), very-low-density lipoprotein (VLDL), low-density lipoprotein (LDL), and high-density lipoprotein (HDL).

(4) *Hydrogen/methane breath testing:* breath testing for SIBO.

(5) *Intestinal mucosal barrier:* detect levels of diamine oxidase (DAO), D-lactic acid (D-lac), and lipopolysaccharide (LPS), and combine with the clinical manifestations to evaluate the function of the intestinal mucosal barrier.

(6) *Quality of life (SF-36 Scores):* The quality of life of the patients before and after treatment will be assessed using SF-36 scores and compared to assess the improvement.

#### 4.3. Analysis of the relationships among the function of intestinal mucosal barrier, SIBO, and NAFLD.

1) To analyze the relationship of DAO, D-lac, LPS, intestinal mucosal barrier dysfunction grade I, II, III, IV within trahepatic fat content in NAFLD patients(possible results: unrelated, positively related, or negatively related).

2) To evaluate the relationship between SIBO and intrahepatic fat content in NAFLD patients (possible results: unrelated, positively related, or negatively related).

3) To assess the relationship of DAO, D-lac, LPS, intestinal barrier function dysfunction grade I, II, III, IV with insulin resistance in NAFLD patients (possible results: unrelated, positively related, or negatively related).

4) To detect the relationship between SIBO and insulin resistance in NAFLD patients (possible results: unrelated, positively related, or negatively related).

5) To explore the relationship of DAO, D-lac, LPS, intestinal barrier dysfunction grade I, II, III, IV and peripheral blood lipids profile and liver biochemical parameters (ALT, AST, GGT) (possible results: unrelated, positively related, or negatively related).

6) To investigate the relationship of SIBO and lipids profile and liver biochemical parameters (ALT, AST, GGT) in NAFLD patients (possible results: unrelated, positively related, or negatively related).

7) To estimate the relationship of DAO, D-lac, LPS, intestinal barrier dysfunction grade I, II, III, IV and NAFLD-FS in NAFLD patients (possible results: unrelated, positively related, or negatively related).

8) To determine the relationship between SIBO and NAFLD-FS in NAFLD patients (possible results: unrelated, positively related, or negatively related).

4.4. To evaluate the therapeutic effects of Compound Zhenzhu Tiaozhi capsules on NAFLD

1) To assess whether the content of intrahepatic fat will decrease after 1 month, 3 months, and 6 months of Compound Zhenzhu Tiaozhi capsule therapy.

i. Compare the therapeutic effects of Compound Zhenzhu Tiaozhi capsules at 1 month, 3 months, and 6 months with the baseline (pre-vs.post-therapeutic effects of Compound Zhenzhu Tiaozhi capsules).

ii. Compare the therapeutic effects in the Compound Zhenzhu Tiaozhi capsule group with that of the other three groups at parallel time points (Compound Zhenzhu Tiaozhi capsules vs. Conventional drugs).

2) To assess whether NAFLD-FS will be alleviated after 1 month, 3 months, and 6 months of Compound Zhenzhu Tiaozhi capsule therapy.

i. Compare the therapeutic effects of Compound Zhenzhu Tiaozhi capsules at 1 month, 3 months, and 6 months with the baseline (pre- vs. post-therapeutic effects of Compound Zhenzhu Tiaozhi capsules).

ii. Compare the therapeutic effects in the Compound Zhenzhu Tiaozhi capsule group with those of the other three groups at parallel time points

(Compound Zhenzhu Tiaozhi capsules vs. Conventional drugs).

3) To assess whether insulin resistance will be improved after 1 month, 3 months, 6 months of Compound Zhenzhu Tiaozhi capsule therapy.

- i. Compare the therapeutic effects of Compound Zhenzhu Tiaozhi capsules at 1 month, 3 months, and 6 months with the baseline (pre- vs. post-therapeutic effects of Compound Zhenzhu Tiaozhi capsules).
- ii. Compare the therapeutic effects in the Compound Zhenzhu Tiaozhi capsule group with those of the other three groups at parallel time points (Compound Zhenzhu Tiaozhi capsules vs. Conventional drugs).

4) To assess whether the lipids profile in peripheral blood and liver biochemical parameters (ALT, AST, GGT) will be reduced after 1 month, 3 months, and 6 months of Compound Zhenzhu Tiaozhi capsule therapy.

- i. Compare the therapeutic effects of Compound Zhenzhu Tiaozhi capsules at 1 month, 3 months, and 6 months with the baseline (pre- vs. post-therapeutic effects of Compound Zhenzhu Tiaozhi capsules).
- ii. Compare the therapeutic effects in the Compound Zhenzhu Tiaozhi capsule group with those of the other three groups at parallel time points (Compound Zhenzhu Tiaozhi capsules vs. Conventional drugs).

4.5 In the Compound Zhenzhu Tiaozhi capsules group, firstly calculate the changes in the related parameters of NALFD and the changes in the function of intestine microbiota, then evaluate whether the two changes are related to each other.

1) Analyze the relationship between the changes in DAO, D-lac, LPS, intestinal barrier dysfunction grade I, II, III, IV and the reduction in intrahepatic fat at 1 month, 3 months, and 6 months of Compound Zhenzhu Tiaozhi capsule therapy (possible results: unrelated, positively related, or negatively related).

2) Analyze the relationship between the change in SIBO and the reduction in intrahepatic fat at 1 month, 3 months, and 6 months of Compound Zhenzhu Tiaozhi

capsule therapy (possible results: unrelated, positively related, or negatively related).

3) Analyze the relationship between the changes in DAO, D-lac, LPS, intestinal mucosal barrier dysfunction I, II, III, IV and the improvement of insulin resistance at 1 month, 3 months, and 6 months of Compound Zhenzhu Tiaozhi capsule therapy (possible results: unrelated, positively related, or negatively related).

4) Analyze the relationship between the change in SIBO and the improvement of insulin resistance at 1 month, 3 months, and 6 months of Compound Zhenzhu Tiaozhi capsule therapy (possible results: unrelated, positively related, or negatively related).

5) Analyze the relationship between changes in DAO, D-lac, LPS, intestinal mucosal barrier dysfunction I, II, III, IV and the changes in the lipids profile in peripheral blood and liver biochemical parameters (ALT, AST, GGT) at 1 month, 3 months, and 6 months of Compound Zhenzhu Tiaozhi capsule therapy (possible results: unrelated, positively related, or negatively related).

6) Analyze the relationship between the change in SIBO and the changes in the lipids profile in peripheral blood and liver biochemical parameters (ALT, AST, GGT) at 1 month, 3 months, and 6 months of Compound Zhenzhu Tiaozhi capsule therapy (possible results: unrelated, positively related, or negatively related).

7) Analyze the relationship between changes in DAO, D-lac, LPS, intestinal mucosal barrier dysfunction I, II, III, IV and the change in NAFLD-FS at 1 month, 3 months, and 6 months of Compound Zhenzhu Tiaozhi capsule therapy (possible results: unrelated, positively related, or negatively related).

8) Analyze the relationship between the change in SIBO and the change in NAFLD-FS at 1 month, 3 months, and 6 months of Compound Zhenzhu Tiaozhi capsule therapy (possible results: unrelated, positively related, or negatively related).

4.6. To estimate the ASCVD risk for all NAFLD patients, and to evaluate whether the therapy of Compound Zhenzhu Tiaozhi capsules improves the risk stratification of ASCVD for NAFLD patients, as well as to compare the therapeutic effects of the study capsules and other conventional drugs. The investigators will estimate the ASCVD risk for NAFLD patients after 1 month, 3 months, and 6 months of

Compound Zhenzhu Tiaozhi capsule therapy, according to *Guidelines for Prevention and Treatment of Dyslipidemia in Adults*.

ASCVD populations with different risk stratifications have different target values of lowering LDL-C / non-HDL-C, as shown in the table below.

Risk Stratification	LDL-C	Non-HDL-C
High-risk	<2.6mmol/L(100mg/dl)	<3.4mmol/L(130mg/dl)
Very high-risk	<1.8mmol/L(70mg/dl)	<2.6mmol/L(100mg/dl)
Note: ASCVD: atherosclerotic cardiovascular disease; LDL-C: low density lipoprotein cholesterol; Non-HDL-C: non-high density lipoprotein cholesterol		

If the baseline of LDL-C is high, as it is difficult to reduce LDL-C level to the basic target value after 3 months of standard treatment with existing lipid-lowering drugs, we propose to lower LDL-C level to at least 50% of baseline as the surrogate target value(IIa recommendation, Level B evidence). There are also some patients at very high-risk who have a baseline LDL-C within the basic target value; for these patients the investigators propose to reduce LDL-C levels to about 30% of baseline (I recommendation, A-level evidence).

Those who meet any of the following criteria can be directly classified as high-risk or very high-risk populations, as indicated:

1. Very high-risk: ASCVD patients (acute coronary syndrome, stable coronary heart disease, revascularization, ischemic cardiomyopathy, ischemic stroke, transient ischemic attack, peripheral atherosclerosis, etc.);
2. High-risk: (1) LDL-C  $\geq 4.9$  mmol/L or TC  $\geq 7.2$  mmol/L, (2) Diabetics: 1.8 mmol/L  $\leq$  LDL-C  $< 4.9$  mmol/L (or) 3.1 mmol/L  $\leq$  TC  $< 7.2$  mmol/L, and age  $\geq 40$  years old.
3. For those who do meet the above criteria, the investigators will evaluate their 10-years ASCVD risk as follows

Number of risk	Stratification of Serum Cholesterol (mmol/L)
----------------	--

factors	3.1 0 TC<4.1(or) 1.8 ≤ LDL-C<2.6	4.1.TC<5.2(or) 2.6 2 LDL-C<3.4	5.2 ≤ TC<7.2(or)3 .4 2 LDL-C<4.9
Without hypertension	Low-risk (<5%)	Low-risk (<5%)	Low-risk (<5%)
0-1	Low-risk (<5%)	Low-risk (<5%)	Moderate risk (5%–9%)
2	Low-risk (<5%)	Moderate risk (5%–9%)	Moderate risk (5%–9%)
3	Low-risk (<5%)	Moderate risk (5%–9%)	Moderate risk (5%–9%)
hypertension	Low-risk (<5%)	Low-risk (<5%)	Low-risk (<5%)
0	Low-risk (<5%)	Moderate risk (5%–9%)	Moderate risk (5%–9%)
1	Moderate risk (5%–9%)	High-risk (≥10%)	High-risk (≥10%)
2	High-risk (≥10%)	High-risk (≥10%)	High-risk (≥10%)
3	High-risk (≥10%)	High-risk (≥10%)	High-risk (≥10%)

4. If the 10-year ASCVD risk is moderate and the age is less than 55 years old, then the investigators propose to do the remaining life assessment. Those who meet any two of the following items can be classified as high-risk: 1.  $\geq 160$  mmHg or diastolic blood pressure  $\geq 100$  mmHg; 2. non-HDL-C  $\geq 5.2$  mmol/L (200 mg/dl); 3. HDL-C  $< 1.0$  mmol/L (40mg/dl); 4. BMI  $\geq 28$  kg/m^2; 5. history of smoking.

3.5. To assess the quality of life using the SF-36 questionnaire for all NAFLD patients, and to evaluate whether the therapy of Compound Zhenzhu Tiaozhi capsules improves the quality of life for NALFD patients, as well as to compare its therapeutic effects with other conventional drugs.

Patients will be required to fill in the SF-36 questionnaire at the time of enrollment, and after 1 month, 3 months, and 6 months of treatment. SF-36 is one of the most widely used and standardized tools for quality of life assessment. SF-36, as a simple health questionnaire, recapitulates the quality of life of the respondents based on eight categories: physiological function, physical pain, general health status, energy, social function, emotional function, and mental health. The first four categories describe physical health, the latter four describe mental health.

The early symptoms of NAFLD are not obvious and almost have no impact on daily life. As it is difficult to effectively assess whether patients have benefited from treatment by evaluating symptoms, the investigators will use the SF-36 questionnaire. The questionnaire will be administered at the time of patient enrollment, and at 1 month, 3 months, and 6 months after treatment. To determine whether drug intervention during the early stage of NAFLD can improve symptoms, the scores of the SF-36 before and after treatment will be compared in the following groups: TLC + metformin, TLC + Compound Zhenzhu Tiaozhi capsules, TLC + simvastatin, and TLC. The four groups will also be compared to one another.

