#### 4. Prescriptions:

4.1: Medications: the dose of Compound Zhenzhu Tiaozhi capsules is 2.52 (4 tablets) tid; metformin is 0.5, tid, and simvastatin is 20mgqn. In general, subjects will be in the hospital for approximately 1 week and continue to receive treatment after discharge from the hospital. The total period of treatment will be 6 months.

4.2: Biochemical assessments: Patients will undergo all the following tests upon admission:

Routine blood test, tumor biomarker tests (alpha-fetoprotein [AFP], carcinoembryonic antigen [CEA], carbohydrate antigen 125 [CA125], and carbohydrate antigen 19-9 [CA19]), uric acid, liver function (representing hepatocyte injury: alanine aminotransferase, aspartate aminotransferase, leucyl aminopeptidase, glutamyl transpeptidase; representing liver secretory function: total bilirubin (TBS), direct bilirubin (DBIL), indirect bilirubin (IBIL); representing liver reserve function: total protein (TP), albumin (ALB), globulin (GLB), and the albumin to globulin ratio (A/G), serum lipid profile (triglyceride, very low density lipoprotein, total cholesterol, low density lipoprotein, high density lipoprotein), FINS (fasting insulin), fasting blood glucose, serum biomarkers of HBV ([i]Hepatitis B surface antigen [HBsAg]; [ii]Hepatitis B surface antibody [anti-HBs]; [iii]hepatitis B e antigen [HBeAg]; [iv]Hepatitis B e antigen antibody [anti-HBe]; [v]Hepatitis B core antibody [anti-HBc]), TP-Ab, syphilis serological test (TRUST), human immunodeficiency virus (HIV), hepatitis C virus antibody,

glycosylated hemoglobin, intestinal mucosal barrier function, coagulation test (prothrombin time [PT], activated partial thromboplastin time [APTT], thrombin time [TT], and fibrinogen [FIB]), Fibrotouch, hydrogen and methane breath test.

4.3 Medical advice on discharge: Physicians need to inform patients regarding the severity of complications in the late stage of NALFD and the importance of early treatment. All the patients should continue treatment after discharge and follow-up in the clinic. They will be required to come back to hospital one month later for re-assessment of the above mentioned items. The appointment telephone number is [name]. The contact doctor is [name].

4.4 All patients will be treated with TLC.

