4.4.1 Dietary advice: On the basis of daily nutrient and energy requirements, if the total amount of saturated fatty and trans fatty acids exceeds the recommended upper limit, unsaturated fats can be used to replace saturated fats. Recommended daily intake of cholesterol is less than 300 mg, especially for ASCVD high-risk patients. The total fat caloric intake should be limited to 20%–30% of the total caloric intake.

[figure not shown]
4.4.2 Controlling weight: Obesity is an important risk factor for dyslipidemia. Energy intake in overweight or obese people with dyslipidemia should be lower than energy consumption to prevent weight increase. The goal is to reduce weight gradually until a normal state is reached. Reducing the total amount of daily caloric intake (daily reduction of 300–500 kcal), improving the diet style, and increasing physical activities can reduce weight by more than 10% for overweight and obese people. It is recommended that patients maintain a healthy weight.

4.4.3 Physical activity advice: It is recommended that patients do moderate-intensity exercises, at least 30 minutes per day for 5 days per week. ASCVD patients should do loading activities first to assess whether they are tolerable, and then do physical activities.

4.4.4 Smoking cessation: Smoking cessation and effective reduction of exposure to second-hand smoke are beneficial to prevent ASCVD and increase serum HDL-C levels.

All smokers can be assisted in the clinics, inquire about smoking cessation through hotlines, or take medication to help with smoking cessation.

4.4.5 Restrictions on drinking: Moderate drinking (male: 20-30 g of ethanol per day, female: 10 - 20 g of ethanol per day) can increase serum HDL-C level. However, even a small amount of drinking can increase TG in patients with high TG. There is no convincing evidence that alcohol can increase cardiovascular disease. It is recommended that patients limit drinking.

Biochemical tests: routine blood test, liver function tests including transaminases, uric acid, FBS, FINS, lipid profile.

Physical examinations: waist circumference, hip circumference, blood pressure, heart rate, BMI

Imaging: abdominal color doppler ultrasound, Fibrotouch

5. Expected results:

1) The liver biochemical parameters and other clinical parameters in NAFLD patients will positively correlate with SIBO and intestinal mucosal barrier function.

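### The capsule arm's before-after change is labelled a therapeutic effect of the capsules, and no text ties the claim that they work to the TLC-only comparison

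*Protocol*

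**What the plan says.** Protocol 4.4, under Endpoints, is headed "To evaluate the therapeutic effects of Compound Zhenzhu Tiaozhi capsules on NAFLD". It covers four outcome groups: intrahepatic fat, NAFLD-FS, insulin resistance, and lipids with liver biochemistry. Each has two items.

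- Item i: "Compare the therapeutic effects of Compound Zhenzhu Tiaozhi capsules at 1 month, 3 months, and 6 months with the baseline". A bracketed note labels this the pre-versus-post therapeutic effect of the capsules.
- Item ii, as worded for the first outcome: "Compare the therapeutic effects in the Compound Zhenzhu Tiaozhi capsule group with that of the other three groups at parallel time points". Its bracketed note describes the comparison as capsules against conventional drugs.

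On what the arms receive, Protocol 3.2 states that "the third group is the TLC + Compound Zhenzhu Tiaozhi capsules group", and 4.4 under Prescriptions adds: "All patients will be treated with TLC".

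The SF-36 section (numbered 3.5, after 4.6) opens its analysis sentence with "To determine whether drug intervention during the early stage of NAFLD can improve symptoms, the scores of the SF-36 before and after treatment". It goes on to list all four groups, TLC among them, for the before-after comparison, and then says the groups will also be compared with one another.

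The expected results (Protocol, item 5) give the capsules' improvement of liver and blood parameters as one result, with no comparator. Superiority over simvastatin and metformin is a separate result. The SAP text available ends at 9.5, baseline characteristics, and contains no efficacy test that settles the matter.

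**The concern.** A change from baseline in an arm on TLC plus capsules combines several things: any capsule effect, the effect of TLC, time trend, regression to the mean in patients enrolled because they have steatosis, and, for a patient-completed scale in an open-label trial, expectation. Item i cannot separate them, yet it is presented as an evaluation of the capsules' therapeutic effect.

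The trial has an arm that can separate them. Capsules + TLC against TLC alone is the one contrast that isolates the capsules. It falls within item ii, but neither the gloss on item ii nor the expected results single it out. The expected results follow the same split as the two items: improvement without a comparator, then superiority over the active drugs. At stake is a statement that the capsules work that rests on before-after change alone, when the difference from TLC alone might be nil.

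**Working it through.** **Inputs from the documents**

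- n = 44 per group, 49 after 10% loss, 196 in total; assumed response rates 69% (P1), 44% (P2 = P3) and 10% (P4); alpha 0.05; "power = 0.80, and a bilateral test" (Protocol 3.1).
- P4 is not labelled. I read it as TLC-only, because P1 is the capsules and P2 = P3 the two standard drugs.
- Response means a drop of at least one level in the fat attenuation index (Protocol 4.1, Primary endpoints).
- NAFLD-FS coefficients: 0.094 per kg/m² of BMI and 0.037 per year of age; BMI cut-offs 28 and 31 (SAP 5).
- Calorie reduction, better diet and more activity "can reduce weight by more than 10% for overweight and obese people" (Protocol 4.4.2).

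**Inputs that are assumptions**

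- The size of the background change in SD units, and the share of patients who worsen.
- A paired t-test and a sign test for item i, since no test is named.

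**Step 1. The plan's sample size.** 44 / 0.9 = 48.9, so 49, and 4 × 49 = 196; both reproduce. The 44 itself does not: a two-sided pooled comparison of 69% with 44% at 80% power gives 61. I take 44 only as the arm size, and the point does not depend on how it was derived.

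**Step 2. What TLC alone could do to one outcome.** At constant height, a 10% weight loss is a 10% fall in BMI. At BMI 28 to 31 that is 2.8 to 3.1 kg/m².

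- Effect on NAFLD-FS: 0.094 × 2.8 = 0.26; 0.094 × 3.1 = 0.29.
- Half a year of ageing adds 0.037 × 0.5 = 0.0185, leaving a net fall of 0.24 to 0.27.

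Item i would count this as a capsule effect even if the capsules did nothing.

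**Step 3. Item i on a continuous outcome, inert capsules.** Paired t-test, n = 44, two-sided 0.05, critical t (43 df) = 2.017, noncentrality = d × √44 = 6.633d, where d is the background mean change divided by the SD of change.

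| d (assumed) | noncentrality | chance of a significant result favouring the capsules |
|---|---|---|
| 0.2 | 1.33 | 25% |
| 0.3 | 1.99 | 49% |
| 0.5 | 3.32 | 90% |

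**Step 4. Item i on level shifts, inert capsules.** Exact two-sided sign test, n = 44, with 10% improving (P4). If nobody worsens, five improvers give p = 2 × 0.5⁵ = 0.0625 and six give 2 × 0.5⁶ = 0.031, so six are needed. P(X ≥ 6) for X ~ Binomial(44, 0.10) is 0.274.

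| improving | worsening (assumed) | chance of a significant result favouring the capsules |
|---|---|---|
| 10% | 0% | 27% (37% at n = 49) |
| 10% | 5% | 5.5% |
| 10% | 10% | 1% |

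**Step 5. Item ii against TLC-only, inert capsules.** Two-sample chi-square test, 44 per arm, by exact enumeration at common response rates of 10%, 20% and 30%. The chance of a significant result favouring the capsules is 3.0%, 2.7% and 2.6% (two-sided 5.9%, 5.4%, 5.3%).

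**Step 6. Can the trial afford to rely on that contrast?** For 69% against 10% with 44 per arm, the pooled rate is 0.395.

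- Null SE = √(2 × 0.395 × 0.605 / 44) = 0.104.
- Alternative SE = √((0.69 × 0.31 + 0.10 × 0.90) / 44) = 0.083.
- (0.59 − 1.96 × 0.104) / 0.083 ≈ 4.6, so power exceeds 99.9%.

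**The case against.** The strongest reply is that the valid analysis is already in the plan. Every item i is paired with an item ii that takes in all three other groups. The sample size is built on a between-arm difference (P1 − P2), and the first primary objective in SAP 2.2 is a comparison with metformin and simvastatin. All of that stands.

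A reader might infer that the plan puts item i first or on a par with item ii, or treats it as sufficient for efficacy. The documents do not support this: 4.4 is a two-item list with no ranking and no decision rule, and list order is not rank. What remains is narrower. Nothing calls item i descriptive, and nothing says which contrast supports the claim that the capsules work.

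A reader might also infer that the SF-36 question is decided on uncontrolled before-after scores. It is not: those scores are shown for the TLC arm as well, and the four groups are compared with one another. Only the stated purpose of the before-after comparison is at fault.

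The list of biases should not be applied uniformly. Selection on steatosis bears most directly on liver fat, and open-label expectation bears more on SF-36 than on laboratory values. Finally, relying on the contrast with TLC alone adds a priority the plan does not state, so the change is slightly more than wording.

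**Conclusion.** The point holds as one of attribution. The before-after change in the capsule arm cannot be credited to the capsules, and the text leaves room to do so. This follows from the design and depends on none of the calculated rates.

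The size is uncertain. For continuous outcomes the chance of a false favourable signal runs from 25% to 90% over assumed background changes of 0.2 to 0.5 SD. For level shifts at the only background rate in the documents (10%, read as TLC-only) it runs from 27% with no worsening to 1% with 10% worsening. The randomized contrast with TLC-only stays near 3% at common response rates of 10% to 30%.

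It would be tempting to headline a false-signal rate of 80%. That needs a background change of 0.43 SD, a value chosen to produce the figure and found nowhere in the documents. The 10% rate does not support it either.

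The change should be made, but the plan does not lack a valid comparison.

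**What to change.** In Protocol 4.4 (1)-(4) and the SF-36 section:

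1. Label within-arm change as descriptive: an estimate with a confidence interval for each arm, and no efficacy claim.
2. State that the claim that the capsules work rests on capsules + TLC versus TLC alone, and the claim that they are better rests on capsules versus metformin and versus simvastatin. Amend the gloss on item ii and the expected results to match.
3. Use the difference in response proportions for the binary primary endpoint, and baseline-adjusted between-arm differences for continuous outcomes.
4. Reconcile SAP 3.1, which lists the drug groups without mentioning TLC, with the protocol, which gives TLC to all arms. The contrast isolates the capsules only if both arms receive TLC.

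The cost is wording and minor analysis work. No new patients, visits or data are needed.
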